## **9.6. Data management**

Data will exist in electronic format for data collected from doctors at visits (e-CRF), and in paper format (CRF) for data collected from patients.

All operations of data management will be performed in agreement with requirements of Pfizer and Standard Operating Procedures of the CRO in charge of data management. The database and a data management manual enabling to define and to describe all activities of biometry will be developed by the CRO and then validated by Pfizer.

### **9.6.1. Case report forms (CRF)/tools for data collection (e-CRF)/electronic recording of data**

As used in this protocol, the term case report forms (CRF)/*e-CRF* should be understood as referring to a paper support medium or to electronic recording of data, or both, depending on method of data collection used in this study.

Data of interest will be recorded in a case report form in electronic format (e-CRF).

A CRF/e-CRF is required and must be completed for each patient included. Original CRF/e-CRF completed are the sole property of Pfizer and must not be made available to any third party in whatever form, except for certified representatives of Pfizer, of appropriate regulatory authorities, without the written authorization of Pfizer. The participating doctor must make certain that CRF/e-CRF are stored in a secure manner on the study site in encrypted electronic format or paper format and will be protected by a password or secured in a locking room in order to prevent unauthorized third parties from accessing them.

The participating doctor is responsible as the last resort for collection and reporting of all clinical data, safety and biological data recorded in the CRF/e-CRF and in all other media for data collection (source documents) and to ensure that they are accurate, authentic/original, attributable, complete, consistent, legible and available if applicable. CRF/e-CRF must be signed by the participating doctor or by a certified member of the research team in order to ensure the authenticity of data entered in the CRF/e-CRF. Any correction made to entries performed in the CRF/e-CRF or source documents must be dated, accompanied by the author's initials and explained (if applicable), and should not conceal the original data entry.

In the majority of cases, source documents are comprised of hospital dossiers or the doctor's dossiers. In this case, data collected in the CRF/e-CRF should correspond to these dossiers.

In some cases, the CRF/e-CRF can also be used as a source document. In this case, a document, available in the participating doctor's centre or at Pfizer, must clearly identify the data which have been recorded in the CRF/e-CRF, and for which the CRF/e-CRF will comprise the source document.

#### **9.6.1.1. Channel of CRF and data entry**

Data collected by the participating doctor at time of inclusion and in the follow-up of patient visits will be recorded directly in the eCRF of the study.

For each centre, a registry will be made available to investigators to list patients eligible but not included: reason for non-inclusion, age, gender, and disease. Only one order number will be used to designate such patients in a manner so that they may be identified. Patients not included will be compared to patients included in the database of characteristics recorded in order to verify the absence of a selection bias or of inclusion bias.

Adverse events will be collected *via* the eCRF by doctors at the usual follow-up consultations, for all patients in the study. When applicable, requests for further information from the Pfizer pharmacovigilance department will be sent to the person who reported the event (participating doctor). All reports (initial and follow-up reports) will be grouped together via a centre number and patient number.

Patients' questionnaires on measurement of compliance and patients' questionnaires on measurement of quality of life will be sent to the CRO in charge of their data entry.

After validation of the database by Pfizer, paper questionnaires will undergo double data entry with the CRO's own software for patients' questionnaires in paper format. Periodic update reports on progression of data entry will be edited by the CRO and sent to Pfizer.

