DATA ANALYSIS	
All tests will be performed with a type 1 error <math>\alpha = 5\%</math>.
 
A descriptive analysis of qualitative and ordinal variables will consist of the sample size and frequency of each modality with its 95% confidence interval (CI). Quantitative variables will be described for the overall population and for each cohort (chronic phase, accelerated phase, blast phase) of patients analyzed, in terms of sample size, mean and medium, standard deviation (SD), confidence interval, as well as number of missing data.
 
An estimate of progression-free survival (PFS) and of overall survival (OS) will be measured by the Kaplan-Meier method. The survival function <math>S(t)</math> will be the probability that the event of interest (progression or death respectively) does not occur before date <math>t</math>. The percent survival will be estimated and described in each of the cohorts of interest.
 
Data will be evaluated separately for patients presenting with chronic phase, accelerated phase or blast phase Philadelphia chromosome +/- CML and depending on treatment line.
 
Interim analyses will be performed if necessary.

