#### **9.4.1.7. Registry of non-inclusion:**

Patients eligible but not included must be recorded in a non-inclusion registry (*see ANNEX 3.7: Registry of non-inclusion*), with a minimum of parameters collected:

- Demographic characteristics (year of birth, gender),
- Reason for non-inclusion.

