## **9.5. Study sample size**

Since the descriptive objective of this study does not involve the hypothesis of specific research, it is not necessary to calculate a minimum sample size population of participating

patients. Furthermore, since CML is a rare disease, a minimum number of patients is not expected.

Based on the number of monthly prescriptions of Bosulif® (sponsor data) and taking into account the future start-up of a competitive study, a total of one hundred (100) patients included in the study appears to be a reasonable objective. Participating doctors should include on average 5 patients in the study, with no distinction between phases of CML at inclusion.

However, it is shown that about one hundred patients would make it possible to have acceptable precision, precision corresponding to half of a 95% confidence interval (CI):

- $\leq 10\%$  to estimate a percent of patients presenting with a given event (Wald asymptotic method without a continuity correction – hypothesis of a 50% rate)
- Of 10% in order to estimate median survival (Greenwood formula under the hypothesis of absence of data censored at the right before median survival and occurrence of a single event at a time).

Consecutive inclusion of patients who satisfy eligibility criteria up to the end of the inclusion period estimated at 2 years will ensure the representativeness of patients in the study.

In order to ensure compliance with this consecutiveness, a registry of non-inclusion will be set up. Patients eligible but not included in the study must be recorded in this registry and throughout the period of inclusion. A minimum of parameters will be collected.

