### **ANNEX 3.7: Registry of non-inclusion**

## **Registry of non-inclusion**

### **OBJECTIVES OF THE REGISTRY OF NON-INCLUSION**

The registry of non-inclusion makes it possible to compare patients who will be included in the BosEVAL study to patients who will not be included.

This comparison makes it possible to have an evaluation of an inclusion bias, as well as to measure their impact on the representativeness of the studied population.

Consequently, the statistical results will be totally utilizable and can be published.

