### **INSTRUCTIONS FOR COMPLETING THE REGISTRY OF NON-INCLUSION**

the registry of non-inclusion is to be completed during the inclusion period of the BosEVAL study for all adult patients who satisfy criteria for inclusion and for non-inclusion but who have not wanted to participate in the study.

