**CHARACTERISTICS OF PATIENTS NOT INCLUDED IN THE STUDY**

CENTRE No.: |\_|\_|

	Date of consultation	Date of birth	Gender	Reason for non-inclusion
1	_ _  /  _ _  /  _ _ _ _  (DD/MM/YYYY)	_ _  /  _ _ _ _  (MM/YYYY)	 Male  Female	 Patient refusal  Other, specify: ____
2	_ _  /  _ _  /  _ _ _ _  (DD/MM/YYYY)	_ _  /  _ _ _ _  (MM/YYYY)	 Male  Female	 Patient refusal  Other, specify: ____
3	_ _  /  _ _  /  _ _ _ _  (DD/MM/YYYY)	_ _  /  _ _ _ _  (MM/YYYY)	 Male  Female	 Patient refusal  Other, specify: ____
4	_ _  /  _ _  /  _ _ _ _  (DD/MM/YYYY)	_ _  /  _ _ _ _  (MM/YYYY)	 Male  Female	 Patient refusal  Other, specify: ____
5	_ _  /  _ _  /  _ _ _ _  (DD/MM/YYYY)	_ _  /  _ _ _ _  (MM/YYYY)	 Male  Female	 Patient refusal  Other, specify: ____

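### The non-inclusion registry allows a comparison on age and gender only, so it cannot verify that selection bias is absent, whatever its size

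*Protocol*

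**What the plan says.** Section 9.6.1.1 provides a registry at each centre to "list patients eligible but not included: reason for non-inclusion, age, gender, and disease". Non-included patients are then compared with included patients on the recorded characteristics "in order to verify the absence of a selection bias or of inclusion bias".

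Section 9.4.1.7 defines the registry content more narrowly: "Demographic characteristics (year of birth, gender") and the reason for non-inclusion. The form in Annex 3.7 has fields for consultation date, month and year of birth, gender and "Reason for non-inclusion". Its instructions say it is for eligible adults "who have not wanted to participate in the study".

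The objectives text in Annex 3.7 says the comparison allows inclusion bias and its impact to be evaluated, and then adds: "Consequently, the statistical results will be totally utilizable and can be published". Section 9.5 says that consecutive inclusion "will ensure the representativeness of patients in the study". Section 9.9.2 (limitations) says that selection of patients by doctors, deliberate or not, cannot be avoided, and presents exhaustive inclusion as a way to limit it.

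**The concern.** Two statements promise more than the comparison can deliver. Section 9.6.1.1 sets out to establish that a bias is absent, and Annex 3.7 draws the favourable conclusion without making it depend on the result. Section 9.9.2 takes the opposite starting point.

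The study's main output is two percentages: patients with a bosutinib-related AE, and patients who stop permanently after one. Section 9.9.2 treats representativeness as the basis for extrapolating them. A report that follows 9.6.1.1 and Annex 3.7 literally would claim that selection bias had been ruled out when the data could not show that.

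**Working it through.** **1. What can be compared**

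| Characteristic | Included patients | Registry: 9.6.1.1 | Registry: 9.4.1.7 | Registry: form |
|---|---|---|---|---|
| Age or birth date | yes | yes | yes | yes |
| Gender | yes | yes | yes | yes |
| Reason for non-inclusion | does not exist | yes | yes | yes |
| Disease | yes | yes | no | no |
| CML phase, treatment line, comorbidities, ECOG | yes | no | no | no |

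Reason for non-inclusion has no counterpart among included patients, so it cannot be compared. Disease is named only in 9.6.1.1. Every eligible patient has CML, so it would add little unless it means phase. Age and gender remain.

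Phase and treatment line are the factors by which section 9.7.1 breaks down the results. If selection acts on a factor that is not recorded and is unrelated to age and gender, a 5% test on age or gender is non-significant about 95% of the time however large the registry is. This step needs no assumption about registry size.

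**2. The plan's own precision figure**

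Section 9.5 gives a 95% CI half-width of at most 10 points for a percentage, with about 100 patients and a 50% rate: 1.96 × √(0.5 × 0.5 / 100) = 9.8 points. It reproduces.

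**3. Age and gender, if the comparison is read as a test**

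Inputs: 100 included (9.5); the Synopsis statement "All tests will be performed with a type 1 error" of 5%, taken as two-sided; 58% male from the 1.4:1 ratio in 7.1 (1.4/2.4 = 58.3%). Assumptions: registry size m, which the protocol does not give, and the true differences (0.5 SD in age; 58% against 38% male).

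- Age: two-sample t-test with noncentrality 0.5 / √(1/100 + 1/m). At m = 10 this is 0.5 / 0.332 = 1.51, and the test misses the difference 68% of the time.
- Gender: pooled two-proportion z-test, with all outcomes enumerated.
- 95% CI half-widths: 1.96 × √(1/100 + 1/m) in SD units for age, and 1.96 × √(0.583 × 0.417 × (1/100 + 1/m)) for gender.

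| m | Age: missed | Gender: missed | Age CI half-width | Gender CI half-width |
|---|---|---|---|---|
| 10 | 68% | 76% | 0.65 SD | 32 points |
| 20 | 47% | 62% | 0.48 SD | 24 points |
| 30 | 34% | 51% | 0.41 SD | 20 points |
| 50 | 18% | 34% | 0.34 SD | 17 points |
| 100 | 6% | 17% | 0.28 SD | 14 points |

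**4. How much a missed difference would matter**

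If the registry holds every eligible non-included patient, the gap between the included sample and all eligible patients is difference × m / (100 + m). For 20 points this is 20 × 10/110 = 1.8 points at m = 10, 20 × 20/120 = 3.3 at m = 20, and 20 × 50/150 = 6.7 at m = 50. For 0.5 SD of age at m = 10 it is 0.5 × 10/110 = 0.05 SD.

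This bound needs a complete registry. The Annex 3.7 instruction speaks of patients unwilling to take part, which is narrower than 9.4.1.7, although the form also offers an other-reason box.

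**The case against.** The strongest reply is that the protocol names no significance test for this comparison. Section 9.6.1.1 says only that the groups are compared, 9.5 and 9.7 describe a study without a test hypothesis, and the Synopsis and 9.7.1 already prescribe 95% CIs. A reader might infer that the plan will take a non-significant result as proof of no bias, and that the miss rates are therefore its error rates. The document does not say so; they apply only if the comparison is done as a test. The method of comparison may also properly sit in the SAP.

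The small-registry argument also cuts both ways. A registry stays small when recruitment is nearly complete, and the possible bias is then small too: 1.8 points at m = 10, against an accepted precision of up to 10 points.

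Nor would an equivalence margin help. At m = 10 the half-widths of 0.65 SD and 32 points lie outside margins such as ±0.5 SD or ±20 points even if the observed difference were zero. Such a rule would deny similarity to a study with almost complete recruitment.

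Finally, the protocol also relies on consecutive inclusion and on comparisons of doctors and centres. Annex 3.7 does mention evaluating bias, and the text is a translation, so the purpose in 9.6.1.1 may have been meant as checking for bias.

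All of this limits the size of the point. It does not rescue the two statements. A descriptive comparison with CIs cannot verify absence of bias either, no SAP can recover variables the form does not collect, and the Annex 3.7 conclusion remains unconditional.

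**Conclusion.** The point holds as one about what the study may conclude. A comparison on age and gender cannot verify that selection bias is absent, at any registry size, and the aim conflicts with section 9.9.2. This follows from the protocol alone.

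The secondary point is conditional on a two-sided 5% test and an assumed registry of 10 to 30: a 0.5-SD age difference would be missed 68% to 34% of the time and a 20-point gender difference 76% to 51%. With 100 in the registry these fall to 6% and 17%.

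A reader might also infer that the primary percentages are biased. Nothing in the protocol shows that. Their calculation is untouched, and a small, complete registry would itself limit the bias. What is overstated is the assurance about generalisability.

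**What to change.** - In 9.6.1.1, replace the aim of verifying absence with *describe and estimate differences between included and non-included patients*.
- Report the number and proportion of eligible patients not included, and the age and gender differences with 95% CIs.
- State that selection on factors the registry does not record cannot be excluded.
- Reconcile disease in 9.6.1.1 with 9.4.1.7 and the registry form, which do not collect it.
- Delete the sentence "Consequently, the statistical results will be totally utilizable and can be published" from Annex 3.7.

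The cost is a few wording changes and one table. The downside is that the report may have to say that representativeness was not shown.

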#### **9.6.1.2. Construction of the database**

An annotated questionnaire will be prepared by the CRO in charge of data management. This document will contain the names of tables and names of variables. Each variable will be associated with its type, its length and possible format. The annotated questionnaire will be submitted to Pfizer for validation.

The CRO then will build a database using its own software. The structure of the database will be documented and verified in listings by comparing the attributes of variables in the database with specifications noted in the annotated questionnaire.

Before entry of real data, the structure of the database and the data entry screens will be tested and validated in agreement with the Standard Operating Procedures of the CRO and those of Pfizer. In order to do this, fictitious questionnaires will be completed and entered. Validation will be performed by a complete examination in listing of these data and then their comparison with data recorded in the questionnaires. A validation report will be sent to Pfizer. The final structure of the database must be submitted to Pfizer for validation before entry of real data.

An audit file will be created to record all changes made to the database. The original data, the modified data, the date and time of the change, the person who made the change and reason for the change will be recorded in the audit file. The operation of the audit file will be tested by change to fictional data. A report will be written and sent to Pfizer.

#### **9.6.1.3. Control of data**

A list of controls of consistency enabling detection of inconsistencies and of aberrant responses present in the questionnaires will be edited by the CRO and validated by Pfizer. Such controls will be scheduled with the CRO's own software and then tested with fictitious data. These fictitious data and the documentation relating to the test will be kept in the study binder by the CRO and available for review by Pfizer.

After data entry, controls will be executed continuously. A specific request for each inconsistency will be generated electronically by the data control system. In order to limit the

number of queries to submit to participating doctors, a guide on obvious corrections prepared by the CRO and validated by Pfizer may be compiled.

The CRO will make available the documentation on control of data upon simple request from Pfizer. Periodic update reports on data control will be edited by the CRO and sent to Pfizer.

#### **9.6.1.4. Access to data**

The database and servers on which they are stored will be located in locking facilities. Only the staff dedicated to the study will have access to the databases.

#### **9.6.1.5. Locking of the database**

Locking of the database will be performed only after data entry, control of data and possible coding has been completed by the CRO. Locking of the database will be performed in agreement with Pfizer procedure CT-24. After validation by Pfizer, the database will be locked by the CRO and readied for statistical analysis.

#### **9.6.1.6. Data management report**

A data management report will be edited by the CRO after locking of the database and sent to Pfizer.

### **9.6.2. Saving of dossiers**

To enable evaluation and/or inspection/audits by the regulatory authorities or by Pfizer, the participating doctor accepts to save dossiers, including the identity of all participating patients (sufficient information to be able to make a link with the dossiers, for example CRF/eCRF and hospital dossiers), all original signed informed consent documents, copies of all CRF/e-CRF, pharmacovigilance report forms, source documents, detailed dossiers on distribution of treatments and adequate documentation on relevant correspondence (for example, letters, minutes of meetings and phone call reports). Dossiers must be saved by the participating doctor in conformity with local regulation or according to specification of the study contract, depending on the longer duration. The participating doctor must make certain that the dossiers continue to be stored in a secure manner as long as they must be stored.

If the participating doctor no longer is able, for whatever reason, to continue to save study dossiers during the period required (for example, in case he retires or moves away), Pfizer must be notified in advance. The study dossiers must be transferred by a person designated by Pfizer, for example another investigator, another institution, or an independent third party named by Pfizer.

The participating doctor's dossiers must be stored for a minimum duration of 15 years after the end or discontinuation of the study or longer if local regulations in force so require.

The participating doctor must obtain written authorization form Pfizer before disclosing any dossier, even if requirements for storage have been satisfied.

## **9.7. Analysis of data**

The detailed methodology for descriptive and statistical analyses of data collected in this study will be documented in a statistical analysis plan (SAP) which will be dated, classified and saved by the sponsor. The SAP can change the plans indicated in the protocol; any major change in definition of the primary evaluation criteria and of their analysis must be translated by a protocol amendment.

Management and statistical analysis of data will be performed using SAS software (version 9.4 or later, SAS Institute, North Carolina USA).

Interim analyses may be performed once a year, if necessary. In case of absence of a test hypothesis, no adjustment for multiplicity therefore is justified.

### **9.7.1. Statistical methods**

#### **Description of data**

Patients' characteristics will be evaluated overall and then separately for patients with CP, AP or BP Ph+/- CML, and by line of treatment. Other data will be separately evaluated for patients presenting with CP, AP or BP Ph+/- CML and then by treatment line.

A descriptive analysis of qualitative and ordinal variables will consist of the sample size and the frequency of each modality with its 95% confidence interval (CI). Quantitative variables will be described in terms of sample size, mean and median, standard deviation, SD, confidence interval.

The description of variables collected during follow-up of each patient will contain a presentation of parameters for each of the times of measurement.

Overall survival data and progression-free survival (PFS) will be described with Kaplan Meier curves. Median survival will be estimated and presented with its 95% CI.

The sample size of missing values for each variable analysed will be indicated in the tables of results. Key data will be made obligatory in the electronic CRF in order to control the percent of missing data, if applicable, with models based on maximization of the function of probability or of techniques of attribution will be used.

#### **Modelling**

- Linear mixed model

PFIZER CONFIDENTIAL

CT24WI-GL02-RF01.1.0 *Model of non-interventional study protocol for study on collection of principal data*

15/08/2018

Page 34 of 79

Linear mixed models for repeated data will be used in the setting of analysis of continuous repeated data (longitudinal analyses). This approach will enable (1) to take into account all data from patients, and (2) to estimate at each measurement time the mean parameter on all of the patients, adjusted to the phase of CML and to treatment line. It will apply to analysis of biological and hematological parameters. The outcome in comparison to baseline (M0) will be estimated by appropriate contrasts.

- Logistical regression

Multivariate logistical regressions (binary variables) or polynomial (multi-categorical variables) will make it possible to estimate the association of qualitative parameters studied (e.g. response) and of explanatory variables (without notion of time). All models used will be adjusted to potential confounding factors or changes to effect.

